8.3.5. Pregnancy

This study is enrolling males and females of non-childbearing potential.

- Details of all pregnancies in female subjects and female partners of male subjects will be collected after the start of study intervention and either until completion of the Follow-up Phone Call on Day 21 or until the details regarding the pregnancy outcome are reported. The CRU should make a reasonable effort to follow any pregnant patients until delivery or end of the pregnancy.
- If a pregnancy is reported, the investigator should inform the sponsor within 24 hours of learning of the pregnancy and should follow the procedures outlined in Appendix 4/Section 10.4.
- Abnormal pregnancy outcomes (eg, spontaneous abortion, fetal death, stillbirth, congenital anomalies, ectopic pregnancy) are considered SAEs.

8.3.6. Cardiovascular and Death Events

Cardiovascular and death events should be reported according to the definitions and reporting procedures for AEs and SAEs outlined in Appendix 3/Section 10.3.

8.3.7. Disease-Related Events and/or Disease-Related Outcomes Not Qualifying as AEs or SAEs

Not applicable to this study in healthy subjects.

8.3.8. Adverse Events of Special Interest

Not applicable to this study

8.4. Treatment of Overdose

For this study, any dose that exceeds the dosage or frequency specified in the protocol will be considered an overdose.

The sponsor does not recommend specific treatment for an overdose.

In the event of an overdose, the investigator should:

1. Report any case of overdose to the sponsor and use their clinical judgment to treat the case of overdose as needed with the appropriate general supportive measures. Subjects will be monitored for potential development of diarrhea and dehydration and, if present, will be managed accordingly.
2. Document the quantity of the excess dose as well as the duration of the overdose in the CRF.

8.5. Pharmacokinetics

Blood for the determination of IW-3300 and metabolites in plasma will be collected from all dosed subjects during the Clinic Period at timepoints specified in the SoA ([Table 1](#)). Instructions for the collection and handling of biological samples will be provided by the sponsor. The actual date and time (24-hour clock time) of each sample will be recorded.

The following PK parameters will be calculated using a noncompartmental approach if a sufficient number of plasma samples exist above lower limit of quantification:

- Area under the plasma concentration time curve from time zero to the time at which the last measurable concentration is observed (AUC_{0-t})
- Area under the plasma concentration time curve from time zero to time infinity ($AUC_{0-\infty}$)
- Maximum plasma concentration (C_{max})
- Time to maximum plasma concentration (T_{max})
- Terminal elimination half-life ($t_{1/2}$)

Blood samples will be analyzed in a single batch after all subjects have completed the study. No individual drug concentration information will be shared until the study has been unblinded.

8.6. Microbiome

Gut microbiome will be assessed using stool samples collected in accordance with the SoA ([Table 1](#)). At Check-in/Day -1, the subject will bring in a stool sample using the sample collection kit issued by the site. Between Day 7 (postdose) through Day 8 (predischarge), the first stool passed will also be collected. If no stool is passed during this time, the subject will be discharged with a stool collection kit and asked to return the sample to the CRU.

The stool collection kit is a tube that contains DNA stabilizer. An aliquot of stool (approximately 1 teaspoonful) will be added to the tube and frozen for analysis.

8.7. Pharmacodynamics

Pharmacodynamics are not evaluated in this study.

8.8. Genetics

Genetics are not evaluated in this study; no samples will be collected for genetics research.

8.9. Biomarkers

Biomarkers are not evaluated in this study; no samples will be collected for biomarker research.

8.10. Immunogenicity Assessments

Immunogenicity is not evaluated in this study; no samples will be collected to evaluate antibodies to IW-3300.

8.11. Medical Resource Utilization and Health Economics

Medical resource utilization and health economics parameters are not evaluated in this study.

9. STATISTICAL CONSIDERATIONS

9.1. Statistical Hypotheses

No hypothesis testing is planned.

9.2. Sample Size Determination

No statistical sample size determination process was performed. The sample size chosen for each cohort (9 subjects) is considered sufficient for evaluation of safety, tolerability, PK, and microbiome.

9.3. Populations for Analyses

The following populations are defined:

Population	Description
Screened Set	The Screened Set consists of all subjects who have signed informed consent.
Intent-to-treat Set	The Intent-to-treat Set consists of all subjects in the Screened Set who have been randomized to a treatment regimen. Analysis will be performed according to the allocated treatment regimen regardless of the treatment regimen actually received.
Safety Analysis Set	The Safety Analysis Set consists of all subjects who receive any amount of study drug. Analysis will be performed according to the treatment actually received regardless of the allocated treatment.
PK Analysis Set	The PK Analysis Set consists of all subjects in the Safety Analysis Set who have at least 1 postdose PK assessment. Analysis will be performed according to the treatment actually received regardless of the allocated treatment.
Microbiome Analysis Set	The Microbiome Analysis Set consists of all subjects in the Safety Analysis Set who have at least 1 postdose microbiome assessment. Analysis will be performed according to the treatment actually received regardless of the allocated treatment.

9.4. Statistical Analyses

The statistical analysis plan (SAP) will be finalized prior to the clinical database lock and will include a more technical and detailed description of the statistical analyses described in this section.

9.4.1. General Considerations

For summaries by treatment group, data from subjects who receive placebo in different cohorts can be combined and presented as one treatment group (referred to as “treatment” and “placebo”), as appropriate.

Continuous variables will be summarized using descriptive statistics (N, mean, SD, median, minimum, and maximum). Categorical variables will be summarized using the count and

proportion of subjects in each category. Furthermore, PK data will be summarized using descriptive statistics, geometric mean, and coefficient of variation (CV%) of the geometric mean.

9.4.2. Primary Endpoints Analyses

The primary endpoint analysis will be based on the Safety Analysis Set.

AE verbatim terms will be coded in the electronic data capture (EDC) system against the most current version of the Medical Dictionary for Regulatory Activities (MedDRA) available at the start of the study.

TEAEs are defined in Section 10.3.1. The TEAEs and TESAEs for 1 calendar day post last dose will be summarized by system organ class, preferred term, and treatment (or cohort).

9.4.3. Secondary Endpoint Analysis

Not applicable to this study

9.4.4. Exploratory Endpoints Analyses

PK analyses will be based on the PK Analysis Set.

Plasma concentrations of IW-3300 and metabolites will be summarized by treatment (or cohort) at each assessment timepoint; additionally, a listing of plasma concentrations will be provided. PK parameters (listed in Section 8.5) will also be calculated for each subject and summarized by treatment, if systemic levels of IW-3300 and/or metabolites are measurable/as data permit (≥ 1 plasma concentration above the lower limit of quantitation [LLOQ] is necessary for calculation of C_{max} and T_{max} ; ≥ 3 plasma concentrations above LLOQ are necessary for calculation of AUC_{0-t} , $AUC_{0-\infty}$, and $t_{1/2}$). Otherwise, the levels of IW-3300 and/or metabolites will not be included for the analysis.

The analysis of the microbiome at the genus level will be based on the Microbiome Analysis Set.

The relative abundance of different phyla, class, order, family, and genera will be constructed and summarized by treatment (or cohort) at baseline and following 7 days of study drug administration using descriptive statistics. Changes from baseline will be calculated.

9.4.5. Safety Analyses

All safety analyses, including the BBMD analyses, will be based on the Safety Analysis Set.

Summaries for the safety parameters corresponding to the primary endpoints (including TEAEs and TESAEs) are described in Section 9.4.2. Additionally, listings will be provided for severe AEs, drug-related AEs, SAEs, and AEs leading to study discontinuation.

Descriptive statistics and changes from baseline at each assessment timepoint will be presented by treatment (or cohort) for the Clinic Period for:

- Clinical laboratory values (in standard units) for each hematology, chemistry, inflammatory marker, and urinalysis parameter
- Vital signs (ie, pulse rate, systolic and diastolic blood pressure, oral temperature, and body weight)

- ECG parameters (ie, heart rate and measures of PR, QRS, QT, and QTcF intervals)
 - Additionally, the overall 12-lead ECG interpretation (normal, abnormal not clinically significant, or abnormal clinically significant) will be summarized.

For the BBMD parameters, descriptive statistics at each assessment timepoint will be presented by treatment (or cohort) for each study period (Screening Period and Clinic Period): BM frequency, stool consistency, fecal incontinence, urinary frequency, urinary urgency, nocturia, and bladder/pelvic pain.

BM-related baseline values will be derived from the BBMD data collected in the Screening Period, specifically, the period of time from 7 days prior to Check-in up to the time of randomization on Day 1. Bladder-related baseline values will be derived from the BBMD data collected predose on Day 1 (with a 24-hour recall). The Clinic Period BM- and bladder-related values will be derived from the BBMD data collected after randomization in the Clinic Period, specifically, the period of time from Day 1 (postrandomization) through Day 8 (Discharge).

9.4.6. Other Analysis/Analyses

Not applicable to this study

9.5. Interim Analyses

No interim analysis is planned for the study. Interim safety reviews are detailed in Section [6.6](#).

9.6. Data Monitoring Committee (DMC)

This study will not utilize a DMC. A Dose Escalation Committee will be utilized to review safety data for each cohort in order to make decisions about dose escalation, as described in Section [6.6](#).

10. SUPPORTING DOCUMENTATION AND OPERATIONAL CONSIDERATIONS

10.1. Appendix 1: Regulatory, Ethical, and Study Oversight Considerations

10.1.1. Regulatory and Ethical Considerations

This study will be conducted in accordance with the protocol and with the following:

- Consensus ethical principles derived from international guidelines including the Declaration of Helsinki and Council for International Organizations of Medical Sciences (CIOMS) International Ethical Guidelines
- Applicable ICH GCP Guidelines
- Applicable laws and regulations

The protocol, protocol amendments, ICF, IB, and other relevant documents (eg, advertisements) must be submitted to an IRB/IEC by the investigator and reviewed and approved by the IRB/IEC before the study is initiated.

Any amendments to the protocol will require IRB/IEC approval before implementation of changes made to the study design, except for changes necessary to eliminate an immediate hazard to study subjects.

The investigator will be responsible for the following:

- Providing written summaries of the status of the study to the IRB/IEC annually or more frequently in accordance with the requirements, policies, and procedures established by the IRB/IEC
- Notifying the IRB/IEC of SAEs or other significant safety findings as required by IRB/IEC procedures
- Providing oversight of the conduct of the study at the site and adherence to requirements of 21 CFR, ICH guidelines, the IRB/IEC, European regulation 536/2014 for clinical studies (if applicable), and all other applicable local regulations

10.1.2. Financial Disclosure

Investigators and subinvestigators will provide the sponsor with sufficient, accurate financial information as requested to allow the sponsor to submit complete and accurate financial certification or disclosure statements to the appropriate regulatory authorities. Investigators are responsible for providing information on financial interests during the course of the study and for 1 year after completion of the study.

10.1.3. Informed Consent Process

The investigator or his/her representative will explain the nature of the study to the subject or his/her legally authorized representative and answer all questions regarding the study.

Subjects must be informed that their participation is voluntary. Subjects or their legally authorized representative will be required to sign a statement of informed consent that meets the requirements of 21 CFR Part 50, local regulations, ICH guidelines, Health Insurance Portability and Accountability Act (HIPAA) requirements, where applicable, and the IRB/IEC or study center.

The medical record must include a statement that written informed consent was obtained before the subject was enrolled in the study and the date the written consent was obtained. The authorized person obtaining the informed consent must also sign the ICF.

Subjects must be reconsented to the most current version of the ICF(s) during their participation in the study.

A copy of the ICF(s) must be provided to the subject or the subject's legally authorized representative.

Subjects who are rescreened are required to sign a new ICF.

10.1.4. Data Protection

All parties will comply with all applicable laws, including laws regarding the implementation of organizational and technical measures to ensure protection of participant data.

Subjects will be assigned a unique identifier by the sponsor. Any subject records or datasets that are transferred to the sponsor will contain the identifier only; subject names or any information which would make the subject identifiable will not be transferred.

The subject must be informed that his/her personal study-related data will be used by the sponsor in accordance with local data protection laws. The level of disclosure must also be explained to the subject who will be required to give consent for their data to be used as described in the ICF.

The subject must be informed that his/her medical records may be examined by clinical quality assurance auditors or other authorized personnel appointed by the sponsor, by appropriate IRB/IEC members, and by inspectors from regulatory authorities.

10.1.5. Committee Structure

Key study personnel, including sponsor and CRO representatives, and their contact details will be provided prior to the Site Initiation Visit.

The safety of this study will be closely monitored on an ongoing basis by sponsor representatives. A Dose Escalation Committee composed of sponsor and CRO representatives will make decisions about dose escalation, as detailed in Section 6.6.

10.1.6. Dissemination of Clinical Study Data

The sponsor will make study results available through www.ClinicalTrials.gov, or other public registries, in accordance with applicable local laws and regulations.

10.1.7. Data Quality Assurance

All subject data relating to the study will be recorded on the eCRF unless transmitted to the sponsor or designee electronically (eg, laboratory data). The investigator is responsible for verifying that data entries are accurate and correct by electronically signing the eCRF.

The investigator must maintain accurate documentation (source data) that supports the information entered in the eCRF.

The investigator must permit study-related monitoring, audits, IRB/IEC review, and regulatory agency inspections and provide direct access to source data documents.

Monitoring details describing strategy (eg, risk-based initiatives in operations and quality such as Risk Management and Mitigation Strategies and Analytical Risk-Based Monitoring), methods, responsibilities, and requirements, including handling of noncompliance issues and monitoring techniques (central, remote, or on-site monitoring) are provided in the Monitoring Plan.

The sponsor or designee is responsible for the data management of this study including quality checking of the data.

The sponsor assumes accountability for actions delegated to other individuals (eg, CROs).

Study monitors will perform ongoing source data verification to confirm that data entered into the CRF by authorized site personnel are accurate, complete, and verifiable from source documents; that the safety and rights of subjects are being protected; and that the study is being conducted in accordance with the currently approved protocol and any other study agreements, ICH GCP, and all applicable regulatory requirements.

Records and documents, including signed ICFs, pertaining to the conduct of this study must be retained by the investigator for the longer of:

- 2 years after the last marketing authorization for the study drug has been approved or the sponsor has discontinued its research with respect to the study drug, or
- Such longer period as required by applicable US regulatory requirements or by US law

No records may be destroyed during the retention period without the written approval of the sponsor. No records may be transferred to another location or party without written notification to the sponsor.

10.1.8. Source Documents

Source documents provide evidence for the existence of the subject and substantiate the integrity of the data collected. Source documents are filed at the investigator's site.

Data reported on the CRF or entered in the eCRF that are transcribed from source documents must be consistent with the source documents or the discrepancies must be explained. The investigator may need to request previous medical records or transfer records, depending on the study.

Definition of what constitutes source data can be found in the Monitoring Plan.

Description of the use of the EDC system is documented in the Data Management Plan.

10.1.9. Study and Site Start and Closure

The first act of recruitment is the date of first subject consent and will be the study start date.

The sponsor designee reserves the right to close the study site or terminate the study at any time for any reason at the sole discretion of the sponsor. The study site will be closed upon study completion. A study site is considered closed when all required documents and study supplies have been collected and a study-site closure visit has been performed.

The investigator may initiate study-site closure at any time, provided there is reasonable cause and sufficient notice is given in advance of the intended termination.

Reasons for the early closure of a study site by the sponsor or investigator may include but are not limited to:

- Failure of the investigator to comply with the protocol, the requirements of the IRB/IEC or local health authorities, the sponsor's procedures, or GCP guidelines
- Inadequate recruitment of subjects by the investigator
- Discontinuation of further study intervention development

If the study is prematurely terminated or suspended, the sponsor shall promptly inform the investigator, the IEC/IRB, the regulatory authorities, and any CRO(s) used in the study of the reason for termination or suspension, as specified by the applicable regulatory requirements. The investigator shall promptly inform the subject and should ensure appropriate subject therapy and/or follow-up.

Study termination is also provided for in the clinical study agreement. If there is any conflict between the contract and this protocol, the contract will control as to termination rights.

10.1.10. Publication Policy

The results of this study may be published or presented at scientific meetings. The sponsor will comply with the requirements for publication of study results. Any publication of data from the study by the investigator will be subject to mutual agreement between the investigator and the Sponsor.

10.2. Appendix 2: Clinical Laboratory Tests

All protocol-required laboratory assessments, as defined below, must be conducted in accordance with the laboratory manual and the SoA ([Table 1](#)).

- The laboratory tests are detailed in [Table 2](#).
- Protocol-specific requirements for inclusion or exclusion of subjects are detailed in Section [5](#) of the protocol.
- Additional tests may be performed at any time during the study as determined necessary by the investigator or required by local regulations.
- The investigator may consider repeating a laboratory test for any subject who has an abnormal laboratory test result (eg, positive hemoccult test, out-of-range chemistry test, abnormal urine culture) at the Discharge (Day 8)/ET Visit. The decision to repeat a laboratory test would be based on the investigator's clinical judgment.

Table 2: Protocol-Required Safety Laboratory Assessments

Laboratory Assessments	Parameters			
Hematology	Platelet count	RBC Indices: MCV MCH MCHC % Reticulocytes		WBC Count with Differential: Neutrophils Lymphocytes Monocytes Eosinophils Basophils
	RBC count			
	Hemoglobin			
	Hematocrit			
Clinical Chemistry ^a	Blood urea nitrogen (BUN)	Potassium	AST	Total and direct bilirubin
	Creatinine	Sodium	ALT	Total protein
	Glucose	Calcium	Alkaline phosphatase	Magnesium
	Chloride	Albumin	Bicarbonate	Phosphate
	Cholesterol	Uric acid		
Inflammatory Markers	
 • ESR • CRP 			
Hemoccult	Point-of-care hemoccult test			
Routine Urinalysis	
 • Specific gravity • pH, glucose, protein, blood, and ketones, by dipstick • Microscopic examination (if blood or protein is abnormal) • Urine culture (if urinary tract infection is suspected) 			
Other Screening Tests	
 • Drug and alcohol screen (to include at minimum: amphetamines, barbiturates, cocaine, opiates, cannabinoids, and benzodiazepines) • FSH • HCG (blood-based test at Screening and urine-based test at Check-in/Day -1) • SARS-CoV-2 testing (Screening and Check-in/Day -1) • HIV antibody and hepatitis panel (HBsAg, and HCV antibody) 			

^a All events of ALT >3×upper limit of normal (ULN) and bilirubin >2×ULN (>35% direct bilirubin) or ALT >3×ULN and international normalized ratio (INR) >1.5, if INR is measured, which may indicate severe liver injury (possible Hy's Law case), must be reported as an SAE (excluding studies of hepatic impairment or cirrhosis).

Investigators must document their review of each laboratory safety report.

Laboratory/analyte results that could unblind the study will not be reported to CRU staff or other blinded personnel until the study has been unblinded.

10.3. Appendix 3: Adverse Events: Definitions and Procedures for Recording, Evaluating, Follow-up, and Reporting

10.3.1. Definition of AE and TEAE

10.3.1.1. AE Definition

- An AE is any untoward medical occurrence in a patient or clinical study subject, temporally associated with the use of study intervention, whether or not considered related to the study intervention.
- NOTE: An AE can therefore be any unfavorable and unintended sign (including an abnormal laboratory finding), symptom, or disease (new or exacerbated) temporally associated with the use of study intervention.

10.3.1.2. TEAE Definition

- A TEAE is an event that emerges, or a pre-existing event that worsens, any time after the initiation of the first dosing of the investigational product.

10.3.1.3. Events Meeting the AE Definition

- Any abnormal laboratory test results (hematology, clinical chemistry, or urinalysis) or other safety assessments (eg, ECG, radiological scans, vital signs measurements), including those that worsen from baseline, considered clinically significant in the medical and scientific judgment of the investigator (ie, not related to progression of underlying disease).
- Exacerbation of a chronic or intermittent pre-existing condition including either an increase in frequency and/or intensity of the condition.
- New conditions detected or diagnosed after study intervention administration even though it may have been present before the start of the study.
- Signs, symptoms, or the clinical sequelae of a suspected drug-drug interaction.
- Signs, symptoms, or the clinical sequelae of a suspected overdose of either study intervention or a concomitant medication. Overdose per se will not be reported as an AE/SAE unless it is an intentional overdose taken with possible suicidal/self-harming intent. Such overdoses should be reported regardless of sequelae.
- Specific Situations
 - AEs that are secondary to other AEs: In general, AEs that are secondary to other AEs (eg, cascade events or clinical sequelae) should be identified by their primary cause, with the exception of severe or serious secondary events. If a medically significant secondary AE that is separated in time from the initiating event occurs, the event may be recorded as an independent event on the AE eCRF after consultation with the sponsor. All AEs should be recorded separately if it is not clear as to whether the events are associated.

- **Persistent AEs:** A persistent AE is one that extends continuously, without resolution, between subject evaluation time points. If the severity changes throughout the duration of the persistent AE, record the severity as it changes.
- **Recurrent AEs:** A recurrent AE is one that resolves between subject visits and subsequently recurs. Each recurrence of the AE should be recorded as a separate AE on the AE eCRF.

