2.3.1. Risk Assessment

Potential Risk of Clinical Significance	Summary of Data/Rationale for Risk	Mitigation Strategy
Study Intervention: IW-3300		
Potential for diarrhea and secondary dehydration	These are class effects of GC-C agonism or effects observed in nonclinical safety pharmacology and toxicology studies of IW-3300.	Intrarectal administration will likely decrease the risk of diarrhea and subsequent dehydration. The study design includes dose escalation to closely monitor subject safety and tolerability at each dose level before dosing with a higher dose; a Dose Escalation Committee will conduct blinded reviews of all the safety parameters of the dosing cohort through Discharge (Day 8) in order to make decisions regarding escalation to the next dose. Orthostatic vital sign measurements will be taken to evaluate the potential for volume depletion. The daily bowel movement (BM) frequency and stool consistency will be monitored in real time to evaluate changes in bowel habits and the potential risk of diarrhea. Stopping rules will also be in place to evaluate continued dosing (Section 7.1.1); dosing within a cohort may be temporarily suspended in the event of a diarrhea or dehydration serious adverse event (SAE); ≥ 1 subject with Grade 3 diarrhea (increase from baseline of >7 stools per day and/or watery stools [Bristol Stool Form Scale {BSFS} score of 7] resulting in a limiting of self-care activities) or dehydration (hospitalization indicated); or ≥ 3 subjects with Grade 2 diarrhea (increase from baseline of 4 to 6 stools per day and/or watery stools [BSFS score of 7] resulting in a limiting of instrumental activities) or dehydration (intravenous fluids indicated).

Potential Risk of Clinical Significance	Summary of Data/Rationale for Risk	Mitigation Strategy

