7.1.1. Study Suspension or Termination

Dosing may be temporarily suspended for either dose level if any of the following occur within a cohort:

- ≥ 1 subject with an SAE considered related to study drug
- ≥ 1 subject with an National Cancer Institute Common Terminology Criteria for Adverse Events (NCI-CTCAE) Grade 3 or higher AE considered related to study drug (CTCAE v5.0 will be used; grading criteria are summarized in Appendix 3/ Section [10.3.3.2](#))
- ≥ 3 subjects with CTCAE Grade 2 or higher AEs considered related to study drug

The Dose Escalation Committee should consider the benefit-risk ratio in their determination to suspend dosing temporarily or permanently. If the benefit-risk ratio is considered unacceptable and the effect related to active study drug by the Dose Escalation Committee, dosing at a given dose level will be stopped, and no additional cohorts will be dosed at the same or higher dose level (a lower dose could still be studied).

The sponsor may permanently terminate the study, or a component of the study, at any time. Reasons for termination may include, but are not limited to:

- Death, SAE, or other safety finding considered to be related to IW-3300 that may preclude further dosing

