Subjects meeting either one of these two criteria and who also have an associated adverse event, as indicated on the eCRF, are considered to be positive for orthostatic hypotension. The number and percent of subjects who have an orthostatic hypotension event will be tabulated by treatment group (or cohort) and by period (baseline versus postbaseline).

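### By default the secondary-AE rule gives non-severe dehydration or orthostatic symptoms caused by diarrhea no AE entry of their own, although Protocol 2.3.1 names secondary dehydration as a risk and lists Grade 2 dehydration in its suspension criterion

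*Protocol*

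**What the plan says.** Protocol 10.3.1.3 states that secondary AEs, in general, "should be identified by their primary cause, with the exception of severe or serious secondary events". Two exceptions follow:

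- For a medically significant secondary AE that is separated in time from the first event, "the event may be recorded as an independent event on the AE eCRF after consultation with the sponsor".
- Where a link between two events is uncertain, each one gets its own record.

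The first entry in the risk table in Protocol 2.3.1 reads "Potential for diarrhea and secondary dehydration". Among the reasons for which dosing within a cohort may be suspended, that entry lists "≥ 3 subjects with Grade 2 diarrhea". The parenthesis that defines the grade then adds dehydration as an alternative with its own definition: "resulting in a limiting of instrumental activities) or dehydration (intravenous fluids indicated".

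Protocol 7.1.1, to which 2.3.1 refers, does not name dehydration. It counts "≥ 3 subjects with CTCAE Grade 2 or higher AEs considered related to study drug".

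Protocol 9.4.2 summarizes TEAEs and TESAEs by system organ class and preferred term. SAP 7.1 adds tables by CTCAE grade and by relationship to study drug. For orthostatic hypotension, SAP 7.3 counts "Subjects meeting either one of these two criteria and who also have an associated adverse event, as indicated on the eCRF".

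**The concern.** The protocol itself describes dehydration as secondary to diarrhea, and secondary events are what 10.3.1.3 by default does not list separately. Section 2.3.1 therefore sets out to count Grade 2 dehydration, while the recording rule generally sends it to the row for diarrhea. No section exempts dehydration or orthostatic symptoms.

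Two things are at stake. The first is the primary endpoint in the detail in which it is reported. With 6 active subjects per cohort, one dehydration event missing from its preferred term is 1/6 = 17% of the arm. The second is that two further counts rely on AE records: the Grade 2 count in 7.1.1 and the orthostatic hypotension table in SAP 7.3. Orthostatic measurements are the protocol's stated check for volume depletion, so a gap there would affect the class effect that the study is watching for.

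**Working it through.** The documents give no figure to reproduce: no hypothesis test is planned and no sample size calculation was made. The check is a comparison of the sections, followed by a conditional illustration.

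**1. Which sequelae are folded into the primary cause?** Protocol 10.3.3.2 labels Grade 2 moderate and Grade 3 severe or medically significant. Applied to an event secondary to diarrhea, 10.3.1.3 gives:

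| Secondary event | Own AE row? |
|---|---|
| Grade 3 or higher, or serious | Yes |
| Grade 1 or 2, not serious, association unclear | Yes |
| Grade 1 or 2, not serious, medically significant, separated in time | Allowed, after sponsor consultation |
| Grade 1 or 2, not serious, clearly and concurrently due to diarrhea | Generally no |

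The last row is the ordinary form of the risk named in 2.3.1.

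**2. Primary TEAE tables.** The diarrhea is itself a TEAE, so the number of subjects with any TEAE is unaffected. Serious secondary events are excepted, so TESAEs are unaffected too. What is lost is the entry for dehydration as a preferred term, with its own grade and causality.

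**3. The count in 7.1.1.** This rule counts subjects, so there are three cases:

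- The diarrhea alone is a related AE of Grade 2 or higher: the subject counts either way.
- The diarrhea alone is Grade 1, but the merged episode is graded 2 or higher because of the dehydration: the subject still counts.
- The merged episode is graded 1: the subject is lost from the count.

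Only the third case matters, and the documents do not say how a merged episode is graded.

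**4. Illustration of the third case.** The rates are assumptions, not figures from the documents. Let d be the probability of related diarrhea of Grade 2 or higher. Let h be the probability of related Grade 2 dehydration with only Grade 1 diarrhea. Suppose merged episodes are graded on the diarrhea alone, no other related Grade 2 AEs occur, and none of the placebo subjects has an event. With 6 active subjects,

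P(at least 3) = 1 − Σ(k = 0 to 2) C(6,k) q^k (1−q)^(6−k),

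where q = d if folded and q = d + h if recorded separately.

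| d | h | Folded | Separate |
|---|---|---|---|
| 0.05 | 0.05 | 0.002 | 0.016 |
| 0.10 | 0.10 | 0.016 | 0.099 |
| 0.20 | 0.20 | 0.099 | 0.456 |

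For d = 0.10 folded: 1 − (0.5314 + 0.3543 + 0.0984) = 0.016. If h = 0, the two columns are equal.

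The only clinical class rates in the documents (Protocol 2.2) are for delayed-release linaclotide: no diarrhea in healthy subjects, and 1.0% to 2.1% diarrhea TEAEs in subjects with IBS-D. At q = 0.021 the probability is about 20 × 0.021³ × 0.979³ = 0.00017, plus a negligible remainder, or about 0.02%. At such rates three subjects would almost never be reached under either recording rule.

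**5. SAP 7.3.** A subject needs a qualifying fall in blood pressure and an associated AE indicated on the eCRF. If dizziness on standing has been folded into diarrhea, the subject is counted only if the eCRF allows the diarrhea record to be marked as the associated AE. The eCRF is not among the documents.

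**The case against.** Recording by primary diagnosis is a conventional choice, and 10.3.3.1 likewise asks for the diagnosis rather than individual signs and symptoms. The rule opens with a general qualifier and has two exceptions. Sequelae can be separated in time, and with daily fasting and enemas the association can be unclear. Protocol 8.3.1 sends laboratory, vital-sign and examination findings to the AE page if they are clinically significant or need intervention. Section 10.3.2 lets the investigator judge as serious an event that needed intervention to prevent a serious outcome.

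A reader might infer that such dehydration is never recorded, so that its recorded incidence is 0% whatever the true rate. These provisions rule that out. They do not remove the default, however: 8.3.1 says when a finding qualifies as an AE, not that a secondary AE gets its own row.

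A reader might also infer that a subject who needs intravenous fluids would stand as Grade 1 diarrhea. Nothing says that the merged event keeps the grade of the stool count, and Grade 1 in 10.3.3.2 means that intervention is not indicated. This objection stands, which is why the effect on 7.1.1 is only conditional.

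Nor would the escalation review see only an AE term. The Dose Escalation Committee reviews all safety and tolerability parameters, including laboratory results and vital signs (Protocol 4.1 and 6). Stool frequency and consistency are followed in real time (2.3.1), and medications are recorded with the reason for use (6.5). Suspension is discretionary. SAP 7.3 lists all vital-sign data in any case. This objection also stands: the gap lies in AE tables and AE-based counts, not in everything the committee sees.

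**Conclusion.** The inconsistency is real but narrow. By default, dehydration or orthostatic symptoms that are neither severe nor serious, and are clearly and concurrently caused by diarrhea, would generally not be recorded as separate AEs, whereas 2.3.1 names and counts such dehydration separately. The firm consequence is under-counting of dehydration by preferred term in the primary TEAE tables. The number of subjects with any TEAE and the TESAE incidence are not affected.

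Two further effects are possible but conditional. The count in 7.1.1 falls only if merged episodes are graded below Grade 2. The SAP 7.3 table loses cases only if the eCRF needs a separate associated AE. Neither effect can be sized from the documents.

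A reader might infer from the illustration that the suspension criterion is badly weakened. The documents do not support that. The assumed rates of 5% to 20% per component lie well above the class rates of 0% to 2.1%, and the illustration also takes for granted the grading convention that the protocol leaves open.

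**What to change.** Reconcile Protocol 10.3.1.3 with 2.3.1, 7.1.1 and SAP 7.3 by adding one sentence to the bullet on secondary AEs, for example: *Dehydration, and orthostatic symptoms or orthostatic hypotension, are recorded as separate AEs with their own CTCAE grade and causality, even when secondary to diarrhea.* Repeat it in the eCRF completion guidance.

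Leave the rule unchanged for other secondary events. Separating every secondary event of Grade 2 or higher would undo much of a conventional rule without need. The suspension criteria are not changed.

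The cost is one sentence and some double listing: one clinical episode may appear under two preferred terms. The number of subjects with any TEAE stays the same.
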